**STUDY SCHEMA**

**STUDY SYNOPSIS**

Title	Phase Ib/II Trial of Interleukin-2 and PD-1 Checkpoint Inhibitor, Nivolumab In Metastatic Clear Cell Renal Cell Cancer
Phase	Phase Ib/II
Methodology	
Single arm, multi-site phase Ib/II clinical trial of standard doses of High Dose Interleukin-2 (HD IL2) (600,000 IU/kg/dose intravenously during two 5-day cycles 9 days apart) in IL-2 eligible clear cell metastatic RCC subjects in combination with Nivolumab.
 
Nivolumab will be administered intravenously at 480 mg/dose over 60 minutes every 28 days, starting 1 week to 3 weeks after the start date of the first cycle of IL2 and continued for up to 48 weeks total in the absence of disease progression by RECIST 1.1 criteria, unacceptable toxicity, withdrawal of consent or lack of clinical benefit as determined by the PI.
 
Nivolumab may be continued beyond 48 weeks off-study at the discretion of the investigator at his or her clinical judgment.
 
Initially 10 patients will be enrolled in the phase 1b portion of the study.
 
The first 3 patients will be treated with sequential (rather than interspersed) treatment. They will receive 2 cycles of HD-IL2 given in standard fashion (two 5-day cycles one week apart) followed by nivolumab starting the week after the second IL-2 cycle and continuing every 4 weeks as per standard nivolumab dosing.
 
We will perform a safety analysis after the first 3 patients are treated. If 2 out of 3 of the first patients suffer a grade 3 or 4 immune related toxicity, the study will stop. The 4th patient will not be enrolled until after the analysis of the 3 patient cohort is complete and submitted to the regulatory bodies.
 
If <2 patients suffer a grade 3 or 4 immune related toxicity, the study will enroll up to 7 more patients treated with Nivolumab administered intravenously at 480 mg/dose over 60 minutes every 28 days, starting 1 to 3 weeks after the start date of the first cycle of IL2. We will monitor these patients continuously for immune mediated dose limiting toxicities for 28 days from the first dose of nivolumab. If, at any time during accrual to the phase1 b portion, 6 patients or more have a grade 3 or 4 immune mediated event of interest (as described in section 5.2.1) we will pause the study and modify/discontinue the protocol in consultation with the site principal investigators and applicable regulatory authorities. If ≤ 5 of the 10 patients have a grade 3 or 4 immune mediated event of interest (as described in section 5.2.1), we will proceed to the phase II portion of the study. Please note: immune mediated events of interest do not include those that are known to occur during high dose IL-2 monotherapy and are reversible by holding IL2 dose(s) such as capillary leak syndrome.

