
Statistical Methodology
	
This is a single arm phase Ib/II trial of Nivolumab and IL-2 in patients with Renal Cell Carcinoma. The phase Ib has an endpoint of safety and the phase II primary endpoint is overall response rate (ORR = CR or PR) at 12 weeks. A recently reported trial of Nivolumab after 1 prior therapy in RCC reported had an ORR of 25%. With the addition of IL-2 treatment to nivolumab, we hypothesize an ORR of approximately 46% in this population.
 
Study Design/Study Endpoints/Sample Size and Accrual  For the phase Ib portion of the study: We will accrue an initial cohort of 3 patients who will be treated with sequential (rather than interspersed) treatment. They will receive 2 cycles of HD-IL2 given in standard fashion (two 5-day cycles one week apart) followed by nivolumab starting the week after the second IL-2 cycle and continuing every weeks as per standard nivolumab dosing. If 2 out of 3 of the first patients suffer a grade 3 or 4 immune related toxicity of interest (see 5.2.1) the study will stop. The 4th patient will not be enrolled until after the analysis of the 3 patient cohort is complete and submitted to the regulatory bodies.
 
If <2 patients suffer a grade 3 or 4 immune related toxicity in the cohort of 3 patients, the study will enroll 7 more patients treated with Nivolumab administered intravenously at 480 mg/dose over 60 minutes every 28 days, starting 1 week to 3 weeks after the start date of the first cycle of IL2. We will monitor these patients continuously for immune mediated dose limiting toxicities for 28 days from the first dose of nivolumab with DLTs being reported as they occur. 10 total patients will be treated and observed for toxicity for 28 days from the first dose of Nivolumab. If, at any time during accrual, 6 patients or more have a grade 3 or 4 immune mediated event of interest (as described in section 5.2.1) we will pause the study and modify/discontinue the protocol in consultation with the site principal investigators and applicable regulatory authorities. If 5 or fewer patients experience grade 3 or 4 immune mediated toxicity of interest (see 5.2.1) during the toxicity window, then the study will continue to the phase II portion. We choose to examine toxicity after 10 patients because if 6 patients or more are found to have a DLT then the 95% exact binomial confidence interval will be > 25% and be indicative that there is too high an incidence of serious immune mediated toxicities.
 
The phase II portion of the trial will be a Simon mini-max 2-stage design. The first stage will accrue 12 patients (INCLUDING any evaluable patients accrued in the phase 1b portion). If more than 2 patients have a response (CR or PR) out of the 12 patients, then we will accrue 11 more patients for a total sample size of 23 evaluable patients. If more than 8 responses (CR or PR) are observed, then we will recommend further study of the combination. This design has 80% power and 10% type I error. If the true ORR of the combined treatment is 25% or less, the probability of early termination of the trial is 39%. If the true ORR is 46% or greater, then the probability of stopping early is only 3.6%. Patients accrued in the Phase Ib portion of the trial will also be included in the Phase II if they are evaluable as defined below.
 
Evaluable Patients: All patients who receive at least 1 dose of IL-2 and at least 1 dose of Nivolumab will be evaluable for the primary endpoint of overall response proportion in the phase II portion of the

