#### **Study Endpoints**

##### **Phase Ib portion:**

Primary Endpoint: To establish that the combination of High Dose Interlukin-2 and Nivolumab is safe and tolerable by monitoring 10 patients for immune mediated grade 3/4 events of interest for 28 days from the first dose of Nivolumab.

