##### **Phase II portion:**

Primary Endpoint: Efficacy of the combination therapy will be determined by the overall response (ORR) rate/proportion with response including complete response rate/proportion as assessed by RECIST 1.1 criteria.

Secondary Endpoints:

Safety will be defined by the frequency of protocol specified therapy-related grade 3-5 adverse events including events of clinical interest for duration of protocol specified therapy and an additional 60 days beyond that, as assessed by NCI's CTCAE version 4.0.

Survival endpoints for efficacy are 24-month Overall Survival (OS) and 24-month Progression-Free Survival (PFS) in subjects treated with the combination by RECIST 1.1 criteria.

To descriptively characterize the circulating immune cell repertoire before and after start of combination therapy with High Dose Interlukin-2 in combination with the immune checkpoint inhibitor Nivolumab

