subject's best interests, it is permissible and will be recorded in follow-up. If so, nivolumab should be held during IL2 weeks. No protocol specified assessments are required for the repeat course.

- 5.1.3 Nivolumab will be administered intravenously at a standard dose of 480 mg/dose every 4 weeks starting on week 2 (ideally day 1 of week 2 but can be given up to 3 weeks after IL-2 start but NOT be on the same week as any HD IL2 cycle) and continued as long as clinical benefit continues as determined by the treating investigator for up to 48 weeks on study.
- 5.1.4. The first 3 patients will be treated with sequential (rather than interspersed) treatment. They will receive 2 cycles of HD-IL2 given in standard fashion (two 5-day cycles one week apart) followed by nivolumab starting the week after the second IL-2 cycle and continuing every 4 weeks as per standard nivolumab dosing.

We will perform a safety analysis after the first 3 patients are treated and if 2/3 patients suffer a grade 3 or 4 immune related toxicity, the study will stop. The 4th patient will not be enrolled until after the analysis of the 3 patient cohort is complete and submitted to the regulatory bodies

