#### 11.1 Study Design/Study Endpoints/Sample Size and Accrual

For the phase 1b portion of the study: We will accrue an initial cohort of 3 patients who will be treated with sequential (rather than interspersed) treatment as follows: they will receive 2 cycles of HD-IL2 given in standard fashion (two 5-day cycles one week apart) followed by nivolumab starting the week after the second IL-2 cycle and continuing every 4 weeks as per standard nivolumab dosing. If 2 or more out of 3 of the first patients suffer a grade 3 or 4 immune related toxicity of interest (see 5.2.1) **within 28 days** from the first dose of nivolumab (**DLT period**) the study will stop. The 4th patient will not be enrolled until after the analysis of the 3 patient cohort is complete and submitted to the regulatory bodies.

If <2 patients suffer a grade 3 or 4 immune related toxicity in the cohort of 3 patients, the study will enroll 7 more patients treated with Nivolumab administered intravenously at 480 mg/dose over 60 minutes every 28 days, starting 1 to 3 weeks after the start date of the first cycle of IL2. We will monitor these patients **continuously** for immune mediated dose limiting toxicities **for 28 days** from the first dose of nivolumab (**DLT period**). Up to 10 total patients will be treated and observed for toxicity for 28 days from the first dose of Nivolumab in the phase 1b portion.

If, at any time during accrual to the phase 1 b portion, 6 patients or more have a grade 3 or 4 immune mediated event of interest (as described in section 5.2.1) we will pause the study and modify/discontinue the protocol in consultation with the site principal investigators and applicable regulatory authorities. If 5 or fewer patients experience grade 3 or 4 immune mediated toxicity of interest (see 5.2.1) during the toxicity window, then the study will continue to the phase II portion.

We choose to examine toxicity after 10 patients because if 6 patients or more are found to have a DLT then the 95% exact binomial confidence interval (26% - 88%) will be > 25% and be indicative that immune mediated toxicity with this regimen is too great.

Dose-Limiting Toxicity is defined as a grade 3 or 4 immune mediated event of interest (as listed and described in section 5.2.1). Please note: immune mediated events of interest do not include those that might occur during high dose IL-2 and are reversible.

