DLT evaluable patients: All patients who receive at least 1 dose of HD IL2 and at least 1 dose of Nivolumab will be evaluable for the primary endpoint of toxicity in the phase Ib portion of the trial. Subjects who are not evaluable will be replaced.

The phase II portion of the trial will be a Simon mini-max 2-stage design. The first stage will accrue 12 patients (including any response evaluable patients accrued in the phase 1b portion). If more than 2 patients have a response (CR or PR) out of the 12 patients, then we will accrue 11 more patients for a total sample size of 23 evaluable patients. If more than 8 responses (CR or PR) are observed in the 23 evaluable patients, then we will recommend further study of the combination. This design has 80% power and 10% type I error. If the true ORR of the combined treatment is 25% or less, the probability of early termination of the trial is 39%. If the true ORR is 46% or greater, then the probability of stopping early is only 3.6%. Patients accrued in the Phase Ib portion of the trial will also be included in the Phase II if they are evaluable as defined below.

Response Evaluable Patients: All patients who receive at least 1 dose of Nivolumab and IL-2 will be evaluable for the primary endpoint of overall response proportion in the phase II portion of the trial. If response at 12 weeks is not recorded for the patient, then the patient will be considered a non-responder.

We expect accrual to the entire study to be completed over a period of 24 months.

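### Read literally, the phase Ib DLT rules leave out an immune-mediated event recorded only as grade 5, which can change a decision at the boundary; separately, the synopsis and 11.1 exclude different events from the DLT

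*Combined protocol and SAP*

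**What the plan says.** Section 11.1 defines the event that drives phase Ib: "Dose-Limiting Toxicity is defined as a grade 3 or 4 immune mediated event of interest (as listed and described in section 5.2.1". The phase Ib primary endpoint uses the same grades: "monitoring 10 patients for immune mediated grade 3/4 events of interest for 28 days from the first dose of Nivolumab". So do the decision rules:

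- Stop after the first cohort (5.1.4): "if 2/3 patients suffer a grade 3 or 4 immune related toxicity, the study will stop". Section 11.1 repeats this as two or more of three and adds the 28-day window.
- Pause (synopsis and 11.1): "6 patients or more have a grade 3 or 4 immune mediated event of interest".
- Go: the synopsis methodology opens phase II when at most "5 of the 10 patients have a grade 3 or 4 immune mediated event of interest". The synopsis statistical section and 11.1 say the same: "If 5 or fewer patients experience grade 3 or 4 immune mediated toxicity of interest (see 5.2.1) during the toxicity window".

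Section 8.8 on stopping rules only refers to 11.1, and the tables in 5.2.1 list no grade above 4. The denominator is set by exposure: "All patients who receive at least 1 dose of HD IL2 and at least 1 dose of Nivolumab will be evaluable". By contrast, the secondary safety endpoint is the "frequency of protocol specified therapy-related grade 3-5 adverse events", and 11.2 uses the same range.

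Two notes limit what counts as an event of interest. The synopsis methodology excludes events that are known with high-dose IL-2 given alone and that reverse when IL-2 doses are held. Section 11.1 excludes events that might occur during high-dose IL-2 and are reversible, and does not say how they must reverse.

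**The concern.** The DLT count is the phase Ib primary endpoint, and it decides whether the trial stops, pauses or opens phase II. Elsewhere the plan writes grade 3-5 when it means to include deaths, so a literal reader can take grade 3 or 4 as a real limit. One dose of each drug makes a patient evaluable. A patient whose only qualifying record is grade 5 would therefore not be replaced and would count as free of DLT. The most serious outcome would then lower the observed DLT proportion.

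The two exclusion notes raise a different problem. If they do not describe the same set of events, the count depends on which page the assessor follows.

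**Working it through.** **1. The plan's own figure.** Exact 95% limits for x events in n patients are the 2.5% quantile of Beta(x, n-x+1) and the 97.5% quantile of Beta(x+1, n-x). For 6/10 this gives 26.2%-87.8%, which reproduces the 26%-88% in 11.1 and lies above the plan's 25% criterion. For 5/10 it gives 18.7%-81.3%, with a lower limit below 25%.

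**2. Boundary cases.** Take one patient recorded only as grade 5.

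| Other patients with a DLT | Count as written | Count if grade 5 is included |
|---|---|---|
| 1 among the first 3 | 1/3: enrol 7 more | 2/3: stop |
| 5 among the 10 | 5/10: open phase II | 6/10: pause |

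With any other number of DLTs, one such patient leaves the decision unchanged.

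**3. Average effect.** The documents give no fatal rate for the combination. Assume a grade-5-only rate of 1 percentage point and a total grade 3-5 rate p of 20%, 25% or 50%, so that the rate counted as written is q = p - 0.01.

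- 2-of-3 rule: S(p) = 3p²(1-p) + p³.
- 6-of-10 rule taken alone: T(p) = P(Bin(10,p) ≥ 6).
- Phase II opens, with the first-3 rule applied: O(p) = Σ over k = 0, 1 of P(Bin(3,p) = k) × P(Bin(7,p) ≤ 5-k).

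| p | S(p) - S(q) | T(p) - T(q) | O(q) - O(p) |
|---|---|---|---|
| 20% | 0.1040 - 0.0946 = 0.9 points | 0.0064 - 0.0049 = 0.1 points | 0.9039 - 0.8940 = 1.0 points |
| 25% | 0.1563 - 0.1452 = 1.1 points | 0.0197 - 0.0161 = 0.4 points | 0.8499 - 0.8378 = 1.2 points |
| 50% | 0.5000 - 0.4850 = 1.5 points | 0.3770 - 0.3526 = 2.4 points | 0.4271 - 0.4072 = 2.0 points |

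**4. Given that such a patient has occurred.** Let the other patients have a grade 3-4 rate of 20%/25%/50% (assumed). If the patient is one of the first 3, the 2-of-3 rule stops with probability p² = 4%/6%/25% as written, against 1-(1-p)² = 36%/44%/75% if grade 5 counts. Now let the patient be equally likely to be any of the 10, and set c = 0 as written or c = 1 if counted. Phase II opens with probability

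0.3 × Σ over j < 2-c of P(Bin(2,p) = j) × P(Bin(7,p) ≤ 5-j-c) + 0.7 × Σ over k = 0, 1 of P(Bin(3,p) = k) × P(Bin(6,p) ≤ 5-k-c).

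This is 91.4%/86.9%/50.6% as written, against 81.3%/74.5%/30.8% if counted.

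**5. The two exclusions, on one case.** Suppose nivolumab is given in week 2 and a grade 3 creatinine rise begins during the second IL-2 cycle (D15-D19, section 5.1.2) and reverses only with steroids. Section 5.2.1.7 lists creatinine elevation as an event of interest, and section 1.2 lists renal failure as an IL-2 toxicity.

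- Synopsis note: the event did not reverse on holding IL-2, so it is not excluded and counts as a DLT.
- Section 11.1 note: the event is of a kind that might occur during IL-2, did begin then, and reversed, so it is excluded.

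In the first 3 patients both IL-2 cycles come before nivolumab, so this conflict concerns patients 4-10.

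**The case against.** The rules count patients who suffer or have a grade 3 or 4 event; they do not classify by worst or final grade. A patient who dies of such an event will usually have met a grade 3-4 description first and can be counted on that basis. This stands, and it narrows the gap to patients for whom no such phase is counted in the window.

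A reader might take the figures in step 4 as the size of the problem. They are not: they presuppose that a grade-5-only patient has occurred. The nearest figure in the documents is a mortality below 1% with high-dose IL-2 in recent trials (section 1.2). That is not a rate for the combination, and it covers deaths of every kind. At an assumed 0.2-point rate, the effects in step 3 fall to about a fifth: 0.2-0.3, 0.03-0.5 and 0.2-0.4 points.

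A reader might also infer that the trial would continue unnoticed after a fatal event. The documents do not support that. Patient 4 waits until the cohort analysis is submitted to the regulatory bodies (11.1). The DSMC meets monthly in phase Ib and site calls are biweekly (12.0). Unexpected related SAEs are notified within 24 hours and go to the FDA (8.5), and the study can be terminated (5.8.8). These safeguards bear on severity, but none of them changes the DLT count.

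On the exclusions, it would go too far to say that the rules in the synopsis statistical section operate without one. They use the term that the notes qualify, so the notes plausibly apply there. Section 5.1.4 is less clear, because it speaks more loosely of immune related toxicity. Section 11.1 may also have been meant as a shortened form of the synopsis note, but as worded it is broader.

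**Conclusion.** Both parts hold in limited form. (a) The phase Ib definition, endpoint and rules omit grade 5. Where no grade 3-4 phase is counted, a literal count falls one short, and at exactly one other DLT in the first 3, or five others in 10, the decision is reversed. Under the assumed 1-point rate and a 20-50% total rate, the average effect is 0.9-1.5 points for the 2-of-3 rule, 0.1-2.4 points for the 6-of-10 rule alone and 1.0-2.0 points for opening phase II. It deserves correction because it touches the gravest outcome in a gating endpoint, not because it is frequent. Nothing here questions the 6-of-10 threshold or its confidence interval, which reproduces. (b) The two exclusion notes differ in substance and can classify the same event in patients 4-10 differently. The documents give no basis for sizing this part.

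**What to change.** 1. Replace grade 3 or 4 with grade 3-5 in the DLT definition, the phase Ib primary endpoint and the phase Ib stop, pause and go rules (synopsis methodology, synopsis statistical section, Study Endpoints, 5.1.4 and 11.1). State in 11.1 that a fatal immune-mediated event of interest, of a type listed in 5.2.1, counts as a DLT, so that the pointer to tables ending at grade 4 does not reopen the gap. Keep the words immune mediated and the exclusion of non-inflammatory causes; without them, deaths unrelated to immune toxicity would count.

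2. The sponsor must reconcile the exclusion notes in the synopsis methodology and 11.1 into one definition, and have the rules in the synopsis statistical section and 5.1.4 refer to it.

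The cost is wording only: thresholds, window and sample size are unchanged. Under item 1, slightly more events may count as DLTs. Item 2 could move some events in either direction.

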### Dosing delays:

- **DURING IL-2 weeks**
  - Individual doses of IL-2 within each cycle may be skipped by the treating investigator at his or her discretion. Skipped doses will not be made up.
  
- **AFTER IL-2, BEFORE NIVOLUMAB**
  - All toxicities (with the exception of fatigue) attributed to IL-2 administration should have resolved or recovered to grade 1 or resolved or to baseline prior to starting nivolumab
  - Fatigue should have recovered to grade 2 or better
  - If toxicities have not improved to the levels listed above, nivolumab and the 2nd cycle of IL-2 should be held until toxicities improve to the above levels
  - If nivolumab or IL-2 is delayed >6 weeks as a result of a toxicity, the subject must be permanently discontinued from study therapy with the following exception:
    - If a steroid taper (to manage drug-related adverse events) is the reason for treatment delay of >6 weeks, and the subject's adverse events recover to grade 1 or better, continuation on study could be possible if approved by the principal investigator
  
- **AFTER NIVOLUMAB, PRIOR TO 2nd IL-2 CYCLE**
  - All immune mediated toxicities should have recovered to grade 1 or better prior to starting the second dose of IL-2 and subjects should be off systemic steroids or on a dose of ≤ prednisone 10mg (or equivalent alternative steroid).
  - Fatigue should have recovered to grade 2 or better
  - If specific toxicities are of unclear attribution (including for example: diarrhea, increased LFTs, cardiovascular disorders, mental status changes, pulmonary disorders and rash) they should be treated as possibly related to nivolumab and treated as per the tables in section 5.2.2. These toxicities must improve to grade 1 or better prior to proceeding with the second week of IL-2 therapy.
  - If toxicities have not improved to the levels listed above, nivolumab and the 2nd cycle of IL-2 should be held until toxicities improve to the above levels

- If nivolumab or IL-2 is delayed >6 weeks as a result of a toxicity, the subject must be permanently discontinued from study therapy with the following exception
  - If a steroid taper (to manage drug-related adverse events) is the reason for treatment delay >6 weeks, and the subject's adverse events recover to grade 1 or better, continuation on study could be possible if approved by the principal investigator
  
- **DURING NIVOLUMAB ONLY TIME PERIOD:**

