  - With any grade 2 or higher **non-hematologic toxicity**, hold nivolumab and refer to section 5.2.1 Events of Interest for relevant management guidelines. If adverse event is not an event of interest and improves to grade 1 or better with symptomatic management and/or supportive medications, nivolumab may be resumed in ≥ 2 weeks. If non-hematologic toxicity does not improve to grade 1 or better within 6 weeks from prior dose, nivolumab should be discontinued.

**5.2.1 IMMUNE MEDIATED EVENTS OF INTEREST (ONCE AT LEAST 1 DOSE OF NIVOLUMAB HAS BEEN ADMINISTERED) - APPLY TO NIVOLUMAB ONLY:**

Certain adverse events that are possibly immune mediated warrant special monitoring and management, and are outlined below to guide investigators.

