**5.2.1.1 Pulmonary:**

Rule out non-inflammatory causes. If non-inflammatory cause, treat accordingly and continue protocol therapy. Evaluate with imaging and pulmonary consultation.

Grade of pneumonitis (NCI CTCAE v4)	Management	Follow-up
Grade 1 Radiographic Changes Only	
 
• Consider delay of nivolumab
 
• Monitor for symptoms every 2-3 days
 
• Consider pulmonary and infectious disease consultations
 
	
 
• Re-image at least every 3 weeks
 
• If worsening, treat as grade 2,3 or 4
 

Grade 2 Mild to moderate new symptoms	
 
• Delay nivolumab
 
• Consult pulmonary and infectious disease
 
• Monitor symptoms daily, consider hospitalization
 
• 1.0mg/kg/day methylprednisolone IV or oral equivalent
 
• Consider bronchoscopy and/or lung biopsy
 
	
 
• Re-image every 1-3 days
 
• Consider prophylactic antibiotics while on steroids
 
• If improves:                             
 
• When symptoms return to near baseline, taper steroids over at least one month
 
• Resume nivolumab and IL-2 if the event improves to grade 0 or 1 within 12 weeks and corticosteroids have been reduced to the equivalent of ≤ 10mg oral prednisone per day
 
 
 
• If not improving after 2 weeks or worsening, treat as grade 3 or 4
 

Grade 3 or 4 Severe new symptoms and/or new or worsening hypoxia
	
 
• Discontinue nivolumab.
 
• Hospitalize
 
• Consult pulmonary and infectious disease
 
• 1-2mg/kg/day methylprednisolone IV or IV equivalent
 
• Add prophylactic antibiotics for opportunistic infections like PCP
 
• Consider bronchoscopy and/or lung biopsy
 
	
 
• If improves to baseline:             
 
• Taper steroids for at least 6 weeks
 
 
 
• If not improving after 48 hours or worsening             
 
• Add additional immunosuppressive agent(s) (e.g. infliximab, cyclophosphamide, intravenous immunoglobulin or mycophenolate mofetil)
 
 
 

---	--	---

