**5.2.1.7 Renal:**

Rule out non-inflammatory causes. If non-inflammatory cause, treat accordingly and continue protocol therapy

Grade of elevation in serum creatinine (NCI CTCAE v4)	Management	Follow-up
Grade 1 Serum creatinine >ULN and >baseline but ≤1.5x baseline	
 
Continue nivolumab
 
Monitor serum creatinine weekly
 
	
 
If returns to baseline, resume creatinine monitoring per protocol
 
If worsens, treat as grade 2, 3, or 4
 

Grade 2 or 3 Serum creatinine 1.5x baseline to ≤ 6 x ULN	
 
Delay or discontinue nivolumab
 
Monitor serum creatinine every 2-3 days
 
0.5-1 mg/kg/day methylprednisolone IV or oral equivalent
 
Add prophylactic antibiotics for opportunistic infections
 
Consider renal biopsy
 
	
 
If improves to grade 1                             
 
Taper steroids over at least one month
 
Resume nivolumab and IL-2 if improves to ≤ grade 1 within 12 weeks and corticosteroids have been reduced to ≤ 10 mg oral prednisone or equivalent per day
 
 
 
If elevation persists >7 days or worsens, treat as grade 4
 

Grade 4 Serum creatinine <6x ULN	
 
Discontinue nivolumab
 
Monitor serum creatinine daily
 
1-2mg/kg/day methylprednisolone IV or IV equivalent
 
Add prophylactic antibiotics for opportunistic infections
 
Consult nephrology
 
Consider renal biopsy
 
	
 
If improves to grade 1                             
 
Taper steroids over at least one month
 
Resume nivolumab and IL-2 if improves to ≤ grade 1 within 12 weeks and corticosteroids have been reduced to ≤ 10 mg oral prednisone or equivalent per day
 
 
 

**For nivolumab only** with any grade 4 **hematologic toxicity**, hold nivolumab. If the adverse event improves to grade 3 or better with symptomatic management and/or supportive medications, nivolumab may be resumed in ≥2 weeks.

Discontinue both IL-2 and Nivolumab permanently for the following conditions:

- Guillain-Barre Syndrome (GBS)
- Myasthenia gravis
- Pituitary apoplexy or hypopituitarism (clinical including based on biochemical values).

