### 6.2.1 Each HD IL2 week (weeks 1 and 3)

- Physical exam, vital signs, ECOG Performance Status, Toxicity.
- Minimum of once daily: urine output measurement, pulse oximetry measurement.
- Hematology: CBC with diff includes total WBC, hemoglobin, hematocrit, platelet count and differential of the WBC including absolute counts
- Serum chemistries: Comprehensive metabolic profile (COMP) includes sodium, potassium, chloride, bicarbonate, BUN, creatinine, AST, ALT, alkaline phosphatase, total bilirubin.
- Magnesium, phosphorus, LDH
- Day 5 and Day 19 (N.B: these will occur during IL2 weeks): Total Creatinine Kinase, Troponin T
- Central line placement prior to any IL2 dose on days 1 and 15.
- HD IL-2 administration will start on Day 1 and continue every 8 hours until Day 5 (cycle 1), then resume on D15 and continue until D19 (cycle 2). HD IL2 dose strength (600,000 IU/kg/dose) will be calculated separately on Day 1 and Day 15 and not modified at other times during the IL2 week. IL2 dose will be administered over 15 minutes ( $\pm$  5 minutes) via a central line.
- Other clinical, laboratory and imaging assessments during HD IL-2 administration as per institutional guidelines per treating investigator

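### The DLT definition in 11.1 leaves out fatal immune-mediated events and severe ones outside the 5.2.1 entries, such as cardiac events

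*Combined protocol and SAP*

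**What the plan says.** The phase Ib primary endpoint is the occurrence of grade 3/4 immune-mediated events of interest in 10 patients over the 28 days from first nivolumab. Section 11.1 turns this into a definition: "Dose-Limiting Toxicity is defined as a grade 3 or 4 immune mediated event of interest (as listed and described in section 5.2.1". It excludes reversible events that might occur during high-dose IL-2. Two rules use the count: stop if 2 or more of the first 3 patients are affected, and pause if 6 or more of 10 are. Section 8.8 refers all stopping rules to 11.1.

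The list that 11.1 relies on opens with "Certain adverse events that are possibly immune mediated warrant special monitoring and management, and are outlined below to guide investigators". Its entries run from "5.2.1.1 Pulmonary" through gastrointestinal, endocrine, hepatic, neurological and skin to "5.2.1.7 Renal". After the renal table come a rule for grade 4 hematologic toxicity and a short list under "Discontinue both IL-2 and Nivolumab permanently for the following conditions": Guillain-Barre syndrome, myasthenia gravis, and pituitary apoplexy or hypopituitarism. There is no cardiac entry and no row for other organs.

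The dosing-delay text in section 5.2 names, as examples of toxicities of unclear attribution, "diarrhea, increased LFTs, cardiovascular disorders, mental status changes, pulmonary disorders and rash". These are to be regarded as possibly due to nivolumab and "treated as per the tables in section 5.2.2". The document has no section 5.2.2.

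The secondary safety endpoint (Study Endpoints and 11.2) counts drug-related events of grades 3 to 5.

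**The concern.** Section 5.2.1 was written as management guidance for selected events. Section 11.1 uses it as a closed endpoint list and limits the grade to 3 or 4. A definition that feeds stopping rules should not exclude the worst outcomes of the kind it is meant to detect. Here a fatal immune-mediated event falls above the grade range, and a severe one in an unlisted organ falls outside the list. Cardiac events are the clearest example, because the protocol itself says cardiovascular toxicity may be due to nivolumab.

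What is at stake is the phase Ib primary endpoint and the decision to move from 3 to 10 patients and then to phase II. With three patients, the classification of one event can decide whether the study stops. Sites working from different sections could classify the same event differently.

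**Working it through.** **1. Which events can be counted.** Set the six examples in section 5.2 against the 5.2.1 tables:

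| Example in 5.2 | Table in 5.2.1 |
|---|---|
| Diarrhea | Gastrointestinal |
| Increased LFTs | Hepatic |
| Mental status changes | Neurological |
| Pulmonary disorders | Pulmonary |
| Rash | Skin |
| Cardiovascular disorders | None |

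Five of the six have a table. The hematologic rule and the three conditions after the renal table add nothing cardiac.

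**2. Wording of the 2-of-3 rule.**

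| Place | Link to 5.2.1? | Grades |
|---|---|---|
| Synopsis, Methodology | No | 3 or 4 |
| Synopsis, Statistical Methodology | Yes | 3 or 4 |
| 5.1.4 | No | 3 or 4 |
| 11.1, stop sentence | Yes | 3 or 4 |
| 11.1, continuation sentence | No | 3 or 4 |

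A grade 4 cardiac event counts under the unlinked wordings and not under the linked ones. A grade 5 event counts under none. The 6-of-10 rule is linked to 5.2.1 in the synopsis and in 11.1.

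**3. The plan's own figure.** The exact (Clopper-Pearson) 95% interval for 6 of 10 is 26.2% to 87.8%, which reproduces the stated 26%-88%. It depends only on 6 and 10, so it does not change with the definition.

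**4. Effect on the 6-of-10 rule.** The documents give no rate for fatal or unlisted events. Assume that a share s of patients with a severe immune-mediated event have only an uncounted one. The counted rate is then p(1 − s), and P(X ≥ 6) is the sum over k = 6 to 10 of C(10,k) q^k (1 − q)^(10−k), with q = p(1 − s).

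| True rate p | s = 0 | s = 10% | s = 20% |
|---|---|---|---|
| 25% | 2.0% (q = 25%) | 1.2% (q = 22.5%) | 0.6% (q = 20%) |
| 50% | 37.7% (q = 50%) | 26.2% (q = 45%) | 16.6% (q = 40%) |

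At 25%, the only toxicity rate the plan uses as a reference, the loss is 0.8 to 1.4 percentage points.

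**5. A second framing.** Hold the listed-event rate at 25% and add an independent grade 3-4 cardiac rate c (assumption). If cardiac events count, the total rate is 1 − 0.75(1 − c). For c = 2%, 5% and 10% this is 26.5%, 28.75% and 32.5%, and P(X ≥ 6) is 2.6%, 3.9% and 6.8%, against 2.0% when they do not count. The chance that the question arises at all in 10 patients is 1 − (1 − c)^10: 9.6%, 18.3%, 40.1% and 65.1% for c = 1%, 2%, 5% and 10%.

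**The case against.** The strongest reply is that these events would not go unseen. Deaths and life-threatening events are SAEs. Unexpected and possibly related SAEs go to the sponsor-investigator within 24 hours and are reported to the FDA. The monitoring committee meets monthly in phase Ib, with biweekly calls across sites, and the fourth patient waits until the three-patient analysis is submitted to regulators. All of this stands: what is lost is the formal count, not the knowledge of the event.

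A limited list is also defensible when IL-2 causes overlapping toxicity and its second cycle can fall inside the DLT window. That supports keeping the IL-2 exclusion. It does not explain leaving out deaths, or leaving out an event that is judged immune-mediated and is not a reversible IL-2 effect.

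Three stronger readings do not hold:

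- A reader might infer that the 2-of-3 rule cannot register a cardiac event. Section 5.1.4 and the synopsis Methodology do not refer to 5.2.1, so on their wording it can. The defect there is inconsistency.
- A reader might take the scheduled cardiac tests as proof that cardiac DLTs were intended. "Total Creatinine Kinase, Troponin T" is measured on Days 5 and 19. Day 5 precedes nivolumab; Day 19 falls in the window only with a week 2 start, and precedes nivolumab in the first three patients. The week 12 echocardiogram comes after the window. The background section lists arrhythmia and hypotension as IL-2 toxicities, which is an equally good reason for these tests.
- A reader might quote the fall from 37.7% to 16.6%. That needs a true rate of 50%, which the plan nowhere names as its limit, and an unsourced 20% share. It also needs no overlap: the rules count patients, so a patient with both kinds of event is counted already. Even with every event counted, the rule misses a 50% rate 62.3% of the time (100 − 37.7); that comes from the threshold, not the list.

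**Conclusion.** The point holds as a defect of definition. Followed literally, 11.1 does not count a fatal immune-mediated event, or a severe one outside the 5.2.1 entries, toward the 6-of-10 pause or its own form of the 2-of-3 stop. This conflicts with the grade 3-5 range used for secondary safety, with section 5.2 on cardiovascular disorders, and with the unlinked wording of the 2-of-3 rule.

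The numerical effect cannot be established from the documents. It is about one percentage point on the chance of reaching 6 of 10 if the true rate is 25% and 10-20% of affected patients are uncounted, and larger at higher true rates; both inputs are assumptions. The case for change rests on the rules excluding the most severe outcomes and on sections that disagree, not on those figures.

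**What to change.** - In 11.1, define a DLT as an immune-mediated event of grade 3 or higher, including grade 5, within 28 days of first nivolumab. Cite 5.2.1 as the reference list but not a closed one, so that immune-mediated events in unlisted organs also count.
- Keep the stated exclusion of reversible IL-2 effects.
- Use the same wording in both parts of the synopsis, in 5.1.4 and throughout 11.1.
- Reconcile the pointer to 5.2.2 with the tables that exist. What applies to cardiovascular events is for the sponsor to decide and state.

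The cost is protocol wording; no new data are needed. The thresholds and the 26%-88% interval are unchanged. The downside is that slightly more events can count as DLTs, and each needs a judgment on whether it is immune-mediated or an IL-2 effect.
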